#### 8. STUDY ASSESSMENTS AND PROCEDURES

The investigator (or an appropriate delegate at the investigator site) must obtain a signed and dated ICD before performing any study-specific procedures.

Study procedures and their timing are summarized in the SoA. Protocol waivers or exemptions are not allowed.

Immediate safety concerns should be discussed with the sponsor immediately upon occurrence or awareness to determine if the participant should continue or discontinue study intervention.

Adherence to the study design requirements, including those specified in the SoA, is essential and required for study conduct.

All screening evaluations must be completed and reviewed to confirm that potential participants meet all eligibility criteria. The investigator will maintain a screening log to record

details of all participants screened and to confirm eligibility or record reasons for screening failure, as applicable.

Every effort should be made to ensure that protocol-required tests and procedures are completed as described. However, it is anticipated that from time to time there may be circumstances outside the control of the investigator that may make it unfeasible to perform the test. In these cases, the investigator must take all steps necessary to ensure the safety and well-being of the participant. When a protocol-required test cannot be performed, the investigator will document the reason for the missed test and any corrective and preventive actions that he or she has taken to ensure that required processes are adhered to as soon as possible. The study team must be informed of these incidents in a timely manner.

For samples being collected and shipped, detailed collection, processing, storage, and shipment instructions and contact information will be provided to the investigator site prior to initiation of the study.

The total blood sampling volume for individual participants in this study is approximately 289.2 mL. Table 3 reflects approximate sample volumes needed for each measured endpoint. The actual collection times of blood sampling may change. Additional blood samples may be taken for safety assessments at times specified by Pfizer, provided the total volume taken during the study does not exceed 550 mL during any period of 30 consecutive days.

Table 3. Blood Volume

Sample Type	Sample	Number of Sampling Times			Total
	Volume (mL)	Screening	Study Period	Follow -Up	Volume (mL)
Safety Labs:					67
FVIII or FIX activity	2.7	1	1		5.4
FVIII or FIX inhibitor a	2.7	1			2.7
Serum chemistry (with Lipid profile a )	4	1	3	0	16
Hematology	2	1	3	0	8
Serology (HbsAg, HBc Ab, HCV Ab, and HIV) a	5	1	0	0	5
APTT, PT/INR, Fibrinogen,	2.7 (combined)	1	3	3	18.9
Anti-thrombin III					
Cardiac Troponin I	3	0	3	0	9
Other Screening a:					10
Protein C activity, protein S level,	5	1	0	0	5
Factor V Leiden mutation, Prothrombin 20210	5	1	0	0	5
mutation					
PK: PF-06741086 concentration	4.5	0	8	3	49.5
Immunogenicity: (ADA, NAb)	9.0	0	1	3	36.0
PD biomarkers:					128.7
TFPI (total and free) levels	2.7	0	8	3	29.7
TGA	2.7	0	8	3	29.7
PF1+2, dPT	4.5 (combined)	0	8	3	49.5
D-dimer	1.8	0	8	3	19.8
TOTAL					289.2

This total volume does not include discarded blood from pre-draws used to remove fluid from flushed, if applicable.

## 8.1. Efficacy Assessments

Not applicable.

#### 8.2. Safety Assessments

#### 8.2.1. Physical Examinations

- A complete physical examination will include, at a minimum, assessments of the head, ears, eyes, nose, mouth, skin, heart and lung examinations, lymph nodes, gastrointestinal, musculoskeletal, and neurological systems. Height and weight will also be measured and recorded. For measuring weight, a scale with appropriate range and resolution is used and must be placed on a stable, flat surface. Participants must remove shoes, bulky layers of clothing, and jackets so that only light clothing remains. They must also remove the contents of their pockets and remain still during measurement of weight.
- A brief physical examination will include, at a minimum, assessments of the general appearance, the respiratory and cardiovascular systems, as well as participant reported symptoms.
- Investigators should pay special attention to clinical signs related to previous serious illnesses.

#### 8.2.2. Vital Signs

- Oral temperature, pulse rate, respiratory rate, and blood pressure will be assessed. Blood pressure and pulse measurements will be assessed in a resting position (either seated or supine) with a completely automated device. Manual techniques will be used only if an automated device is not available.
- Blood pressure, respiratory rate, and pulse measurements should be preceded by at least 5 minutes of rest for the participant in a quiet setting without distractions (eg, television, cell phones).
- Respiratory rate should be measured by observing and counting the respirations of the participant for 30 seconds and multiplied by 2. When blood pressure is to be taken at the same time, measurement should be done during the 5 minutes of rest and before blood pressure measurement.
- No eating, drinking, or smoking is allowed for 15 minutes prior to the measurement of oral temperature.
- Vital signs (to be taken before blood collection for laboratory tests) will consist of 1 pulse and 3 blood pressure measurements (3 consecutive blood pressure readings will be recorded at intervals of at least 1 minute). The average of the 3 blood pressure readings

<sup>a at Screening only.

will be recorded on the CRF.

#### 8.2.3. Electrocardiograms

- Single 12-lead ECG will be obtained as outlined in the SoA (see Section 1.3) using an ECG machine that automatically calculates the heart rate and measures PR, QRS, and QT intervals.
- At each time point at which triplicate ECG are required (ie, when single ECG is abnormal or when troponin I is abnormal), 3 individual ECG tracings should be obtained approximately 2-4 minutes apart.

Single 12-lead ECGs are performed for all participants in a supine position. If a single time point ECG is abnormal (see Appendix 7 for examples of abnormal results), then a triplicate ECG is required. When done in triplicate, ECGs will be obtained approximately 2-4 minutes apart; the average of the triplicate ECG measurements collected at pre-dose Day1 will serve as each participant's baseline value.

Sites with the cTnI assay available at their local laboratory will collect cTnI samples for central and local analysis. If cTnI results are abnormal, the investigator should consult with a cardiologist concerning cTnI and ECG results, and outcome of cardiac consult is then discussed with the Pfizer medical monitor to determine appropriate course of action. When possible, the participant should return within 24 hours for repeated cTnI sample collection.

In some cases, it may be appropriate to repeat abnormal ECGs to rule out improper lead placement as contributing to the ECG abnormality. It is important that leads are placed in the same positions each time in order to achieve precise ECG recordings.

ECG values of potential clinical concern are listed in Appendix 7.

#### 8.2.4. Clinical Safety Laboratory Assessments

See Appendix 2 for the list of clinical safety laboratory tests to be performed and the SoA for the timing and frequency.

The investigator must review the laboratory report, document this review, and record any clinically relevant changes occurring during the study in the AE section of the CRF. Clinically significant abnormal laboratory findings are those which are not associated with the underlying disease, unless judged by the investigator to be more severe than expected for the participant's condition.

All laboratory tests with values considered clinically significantly abnormal during participation in the study or within 28 days after the last dose of study intervention should be repeated until the values return to normal or baseline or are no longer considered clinically significant by the investigator or medical monitor.

If such values do not return to normal/baseline within a period of time judged reasonable by the investigator, the etiology should be identified and the sponsor notified.

All protocol required laboratory assessments, as defined in Appendix 2, must be conducted in accordance with the the SoA.

If laboratory values from non-protocol specified laboratory assessments performed at the institution's local laboratory require a change in participant management or are considered clinically significant by the investigator (eg, SAE or AE or dose modification), then the results must be recorded in the CRF.

Any remaining serum/plasma from samples collected for clinical safety labs at baseline and at all times post-dosing may be retained and stored for the duration of the study.

## 8.2.5. Injection Site Reaction

Injection site reactions will be assessed after single dose of PF-06741086 and according to the Schedule of Activities. Injection site reactions will be measured using the Common Terminology Criteria for Adverse Events (CTCAE), Version 5.0. These measurements will be categorized by CTCAE Grades 1-5 (Table 4).

 Table 4.
 Common Terminology Criteria for Adverse Events for Injection Site Reactions

Grade 1	Tenderness with or without associated symptoms (eg, warmth, erythema, itching)
Grade 2	Pain, lipodystrophy, edema, phlebitis
Grade 3	Ulceration or necrosis, severe tissue damage, operative intervention indicated
Grade 4	Life-threatening consequences, urgent intervention indicated
Grade 5	Death

If deemed appropriate by the investigator, a consultation with a dermatologist will be performed. Documentation may include a dermatologist report, clinic notes and photographs.

#### 8.3. Adverse Events and Serious Adverse Events

The definitions of an AE and an SAE can be found in Appendix 3.

AEs will be reported by the participant (or, when appropriate, by a caregiver, surrogate, or the participant's legally authorized representative).

The investigator and any qualified designees are responsible for detecting, documenting, and recording events that meet the definition of an AE or SAE and remain responsible to pursue and obtain adequate information both to determine the outcome and to assess whether it meets the criteria for classification as an SAE or that caused the participant to discontinue the study intervention/study (see Section 7).

In addition, the investigator may be requested by Pfizer Safety to obtain specific follow-up information in an expedited fashion.

## 8.3.1. Time Period and Frequency for Collecting AE and SAE Information

The time period for actively eliciting and collecting AEs and SAEs ("active collection period") for each participant begins from the time the participant provides informed consent, which is obtained before the participant's participation in the study (ie, before undergoing any study related procedure and/or receiving investigational product), through and including a minimum of 42 calendar days after the last administration of the study intervention.

Follow-up by the investigator continues throughout and after the active collection period and until the AE or SAE or its sequelae resolve or stabilize at a level acceptable to the investigator, and Pfizer concurs with that assessment.

For participants who are screen failures, the active collection period ends when screen failure status is determined.

If the participant withdraws from the study and also withdraws consent for the collection of future information, the active collection period ends when consent is withdrawn.

If a participant definitively discontinues or temporarily discontinues study intervention because of an AE or SAE, the AE or SAE must be recorded on the CRF and the SAE reported using the CT SAE Report Form.

Investigators are not obligated to actively seek AEs or SAEs after conclusion of the study participation. However, if the investigator learns of any SAE, including a death, at any time after a participant has been discharged from the study, and he/she considers the event to be reasonably related to the study intervention, the investigator must promptly report the SAE to Pfizer using the CT SAE Report Form..

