Investigational Product administration				X													
CRU confinement		X	$\rightarrow$	$\rightarrow$	$\rightarrow$	$\rightarrow$	$\rightarrow$	$\rightarrow$	$\rightarrow$	$\rightarrow$	$\rightarrow$	$\rightarrow$	X				
PK blood sampling PD blood sampling h			X		X		X		X	X	X	X	X	X	X	X	
PT/INR	X		X							X			X	X	X	X	
APTT	X		X							X			X	X	X	X	
Fibrinogen	X		X							X			X	X	X	X	
Anti-thrombin III	X		X							X			X	X	X	X	
Cardiac Troponin I			X							X		X					
Immunogenicity (ADA, NAb)			X											X	X	X	
Monitoring injection site reactions				X	$\rightarrow$	$\rightarrow$	$\rightarrow$	$\rightarrow$	$\rightarrow$	$\rightarrow$	$\rightarrow$	$\rightarrow$	X				
Collect information on new bleeding episodes	X	$\rightarrow$	$\rightarrow$	$\rightarrow$	$\rightarrow$	$\rightarrow$	$\rightarrow$	$\rightarrow$	$\rightarrow$	$\rightarrow$	$\rightarrow$	$\rightarrow$	$\rightarrow$	$\rightarrow$	$\rightarrow$	$\rightarrow$	X

Protocol Activity	Screening			Clinical confinement										Follow-up Visits				
Visit Identifier	Screening	Day -1			]	Day 1				Day 2	Day 3	Day 4	Day 7 k	Day 14	Day 21	Day 28 i	Day 42 j	
Visit Window	Day -35 to Day -2												±1 day	±2 days	±2 days	±3 days	±7 days	
Planned Time Pre/Post Dose			-2 hr to -5 min	0 hr	1 hr ±10 min	2 hr ±10 min	4 hr ±20 min	8 hr ±0.5 hr	l .	24 hr ±2 hr		72 hr ±7 hr						
Serious and non-serious adverse event monitoring	X	$\rightarrow$	$\rightarrow$	$\rightarrow$	$\rightarrow$	$\rightarrow$	$\rightarrow$	$\rightarrow$	$\rightarrow$	→	$\rightarrow$	$\rightarrow$	$\rightarrow$	$\rightarrow$	$\rightarrow$	$\rightarrow$	X	
Concomitant medication	X	$\rightarrow$	$\rightarrow$	$\rightarrow$	$\rightarrow$	$\rightarrow$	$\rightarrow$	$\rightarrow$	$\rightarrow$	$\rightarrow$	$\rightarrow$	$\rightarrow$	$\rightarrow$	$\rightarrow$	$\rightarrow$	$\rightarrow$	X	

Abbreviations:  $\rightarrow$  = ongoing/continuous event; ADA = anti-drug antibodies; APTT = activated partial thromboplastin time; CRU = clinical research unit; ECG = electrocardiogram; HBc Ab = hepatitis B core antibody; HBs Ag = hepatitis B surface antigen; HCV Ab = hepatitis C antibody; HIV = human immunodeficiency virus; hr = hours; min = minutes; N/A = not applicable; NAb = neutralizing antibodies; PK = pharmacokinetic; PT/INR = prothrombin time/international normalized ratio

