- a. The full physical examination (PE) planned for Screening may be performed on Day -1 before dosing at the discretion of the Investigator. If a full PE is done at Screening visit, then a brief PE is to be conducted on Day-1. After Day -1, brief examinations based on signs and symptoms will be performed if clinically indicated at the discretion of the Investigator to assess changes from baseline/previous visits of any ongoing symptoms.
- b. Vital signs to be assessed include pulse rate, respiration rate, temperature, and supine blood pressure.
- c. Differential hematology panel required at Screening, Day 1, and Day 7. Differential is optional at additional timepoints, as clinically indicated.
- d. Participants must be fasting for 12 hours prior to blood draw.
- e. A single sample to measure FVIII or FIX activity is to be collected after minimum washout period completed for prescribed factor-replacement product: FVIII replacement therapy for at least 72 hours; Extended half-life FVIII replacement therapy for at least 4× half-life; FIX replacement therapy for at least 4× half-life; bypass agent therapy from rFVIIa, prothrombin complex concentrate (PCC) or activated prothrombin complex concentrate (aPCC) for at least 72 hours.
- CD4 cell count test if HIV positive.
- g. Triplicate ECGs will be obtained at baseline pre-dose on Day 1. Single ECGs will be required at all additional timepoints unless ECG or troponin I is abnormal, in which case a triplicate ECG is required.
- PD blood sample including assessments for: Tissue factor pathway inhibitor (TFPI) (total and free), Thrombin Generation Assay (TGA), Prothrombin fragment 1+2 (PF1+2),
   D-dimer, Dilute prothrombin time (dPT).
- i. Participants with positive ADA results may be requested to return for additional follow-up visits after final planned follow-up visit.
- j. The follow-up Visit at Day 42 could be a Phone Follow-Up visit or a face to face clinic visit at the discretion of the investigator.
- k. Assessments for study early discontinuation or termination refer to Day7 visit. To note that cTnI should be assessed if discontinuation/termination occurs prior to Day 4. ADA and NAb sample will be also collected in case of study early discontinuation or termination.

PF-06741086 B7841010 Final Protocol Amendment 1 22-Oct-2020

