#### 4. STUDY DESIGN

### 4.1. Overall Design

This is a Phase 1, single-arm, open-label, non-randomized, non-controlled, multicenter, study in 6 Chinese adult participants between ages 18 to <75 years with severe hemophilia A or B (defined as Factor VIII (FVIII) or Factor IX (FIX) activity <1%, respectively), with or without inhibitor. This study aims to evaluate the PK, PD, safety and tolerability of a single subcutaneous (SC) dose of PF-06741086.

Approximately 6 participants are planned for enrollment at 2 study sites. Participants who are withdrawn for any reasons may be replaced at the discretion of the investigator and after consultation with the sponsor. Participants will be screened within 35 days prior to administration of the investigational product to confirm that they meet the participant selection criteria for the study. Participants will be admitted into the Clinical Research Unit (CRU) 1 day prior to dosing (Day-1) and will accept a single SC injection of 300 mg PF-06741086 (150 mg \*2) at Day 1. There is no dose modification plan during the study. Participants will be required to stay in the CRU through completion of the Day 7 evaluations. After that, it will be at investigator's discretion on whether the participants should stay in the CRU or not. All participants will return for weekly clinic visits on Day 14, Day 21, and Day 28 per the Schedule of Activities. The follow-up Visit at Day 42 could be a Phone Follow-Up visit or a face to face clinic visit at the discretion of the investigator

Participants who experience a treatment-related adverse event (including lab abnormalitie

s) at any time point will continue to be followed through resolution or stabilization of the event as agreed upon by the investigator and sponsor.

The maximum total duration of the study for a single participant, from initial screening to final follow-up, will be approximately 2.5 months.

CCI

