#### 4.2. Scientific Rationale for Study Design

Study B7841010 will be conducted in Chinese adult participants 18 to <75 years of age with severe hemophilia A or B, with or without inhibitor. This population also matches the entry criteria for the global pivotal Phase 3 study. The mechanism of action of PF-06741086 through the extrinsic cascade predicts it would be effective in both forms of hemophilia. Similarly, it is acceptable to enroll both those with inhibitors and those without, because the mechanism of action is not expected to be influenced by the presence of inhibitors to either FVIII or FIX. The clinical risk/benefit profile for this population is considered appropriate for the evaluation of PK, PD, safety and tolerability of PF-06741086.

The primary objective of Study B7841010 is to evaluate the safety and tolerability of a single SC dose of PF-06741086. Secondary objectives include evaluating the PK, PD properties and immunogenicity of PF-06741086. Selection of the PD endpoints and sampling schedule are based on results from non-clinical studies, the Phase 1 FIH study and Phase 1b/2 first-in patient (FIP) study results. They will reflect either target binding by PF-06741086 (ie, TFPI [total and free] levels) or downstream pharmacologic effects of TFPI inhibition (ie, dPT, TGA, PF1+2 and D-dimer). Thrombosis is a potential risk for inhibition of TFPI, and PF-06741086 is expected to significantly inhibit TFPI, particularly at the highest dose levels. To minimize this risk, hemophilia patients with a known history of thrombotic, ischemic or coronary artery disease, or known pro-thrombotic conditions (eg, Protein C deficiency) will be excluded from this study. Safety monitoring will include laboratory parameters that may be modulated due to coagulopathy (eg, [PT]/INR, APTT, fibrinogen, ATIII and platelet counts) and parameters to screen for possible thrombotic events (eg, cardiac troponin I). Laboratory endpoints to detect excessive modulation of the coagulation pathway will be monitored during the period of peak drug exposure, until at least 28 days have passed since the investigational drug administration.

Potential risks for treatment with PF-06741086 are thrombi or emboli. Depending on location and severity, thrombi or emboli may be life threatening or fatal. An additional potential risk for treatment with PF-06741086 is ADA-induced hypersensitivity. Additional safety information for PF-06741086 is available in the IB.

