#### 4.4. End of Study Definition

A participant is considered to have completed the study if he has completed all phases of the study including the last scheduled procedure shown in the schedule of activities.

The end of the study is defined as the date of the last visit of the last participant in the study or last scheduled procedure shown in the schedule of activities for the last participant in the trial globally.

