3. ENDPOINTS AND BASELINE VARIABLES: DEFINITIONS AND CONVENTIONS

3.1. Primary Endpoints

- Frequency, severity and causal relationship of TEAEs and withdrawals due to TEAE; Day 1 up to Day 42.
- Frequency and magnitude of abnormal laboratory findings (including hematology, PT/INR, APTT, chemistry, urinalysis, fibrinogen, ATIII activity and cTnI); Day 1 up to Day 28.
- Changes from baseline in vital signs (blood pressure, pulse rate, temperature and respiration rate) measurements, 12-lead ECG parameters and physical examination; Day 1 up to Day 28.
- Frequency, severity and causal relationship of injection site reactions; Day 1 up to Day 7.

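### The Day 42 ±7 final contact can fall on Day 35, so neither the 42-day minimum for adverse event collection nor the Day 1 to 42 primary window is guaranteed

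*Protocol*

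**What the plan says.** **Required collection period.** Protocol Section 8.3.1 runs active collection of adverse events and serious adverse events from consent "through and including a minimum of 42 calendar days after the last administration of the study intervention". The same section adds: "Investigators are not obligated to actively seek AEs or SAEs after conclusion of the study participation".

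**Primary endpoint.** SAP Section 3.1 lists "Frequency, severity and causal relationship of TEAEs and withdrawals due to TEAE; Day 1 up to Day 42". Protocol Section 3 gives the same window. SAP Section 6.5.4 summarises bleeding events over Day 1 to Day 42.

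**Schedule.** Protocol Section 4.1 places the single dose on Day 1. The Schedule of Activities (Section 1.3) gives the last visit as Day 42 with a window of ±7 days. The row "Serious and non-serious adverse event monitoring" ends at that visit, as does the row for new bleeding episodes. On its format: "The follow-up Visit at Day 42 could be a Phone Follow-Up visit or a face to face clinic visit at the discretion of the investigator".

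**End of participation.** Under Section 4.4 a participant has completed when all phases are done, "including the last scheduled procedure shown in the schedule of activities". No minimum number of elapsed days is attached.

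**A parallel sentence.** Section 4.2 says laboratory endpoints for excessive modulation of coagulation will be monitored "until at least 28 days have passed since the investigational drug administration". The last coagulation samples are at Day 28 ±3 days.

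**The concern.** Section 8.3.1 states a minimum, and the schedule that sites follow sets a symmetric window around a day that is itself slightly below that minimum. A site can comply fully with the schedule and still stop collecting before the minimum has passed.

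The period affected belongs to the first primary endpoint. A participant whose last contact is on Day 35 has no systematic ascertainment on Days 36 to 42, yet enters the frequency table exactly like one followed to Day 49. SAP Section 5.2 reports numbers and percentages of subjects. SAP Section 3.5.1 ties treatment emergence to an effective duration of treatment without giving a number of days. SAP Section 5.3 refers missing safety data to sponsor standards that it does not spell out. The SAP text therefore contains no rule for a last contact before Day 42 and no report of the days actually observed. With about 6 participants, one unrecorded event would visibly change the reported frequency.

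**Working it through.** This is calendar arithmetic; no sampling formula applies.

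**Inputs**
- Dose on Day 1 (Protocol Section 4.1).
- Day numbering: the Schedule of Activities puts 24 hr on Day 2, 48 hr on Day 3 and 72 hr on Day 4. Hence days after dose = study day − 1.
- Last contact: Day 42 ±7, that is Day 35 to Day 49 (Section 1.3).
- Required minimum: 42 calendar days after dose (Section 8.3.1).
- Endpoint window: Day 1 to Day 42 (Protocol Section 3; SAP Sections 3.1 and 6.5.4).

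**Check of the day counting.** Screening at Day −35 is 35 days before Day 1 if there is no Day 0. 35 + 42 = 77 days, and 77 / 30.44 = 2.5 months, which agrees with the stated study duration.

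**Results for the final contact**

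| Contact | Days after dose | Short of 42 elapsed days | Endpoint days not covered |
|---|---|---|---|
| Day 35 (earliest) | 35 − 1 = 34 | 42 − 34 = 8 | 42 − 35 = 7 |
| Day 42 (on time) | 42 − 1 = 41 | 42 − 41 = 1 | 0 |
| Day 49 (latest) | 49 − 1 = 48 | 0 | 0 |

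- Permitted contact days: 49 − 35 + 1 = 15.
- Days that cover the endpoint window (Day 42 to 49): 8 of 15.
- Days that meet the Section 8.3.1 minimum (Day 43 to 49): 7 of 15.
- If the dosing day is counted as day 1 of follow-up, the earliest contact gives 35 days, still under 42.

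**Ceiling on the loss.** Per participant: 7 / 42 = 16.7% of the endpoint window. Across 6 participants: 6 × 7 = 42 of 6 × 42 = 252 participant-days. The second figure requires all six to be seen on Day 35.

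**Does anything else close the gap?**
- Unplanned visits (Section 1.3) are at the investigator's choice.
- Call-back of participants with positive anti-drug antibodies (schedule footnote i) is optional and limited to them.
- Follow-up to resolution (Sections 8.3.1 and 8.3.3) concerns events already identified.
- After participation ends, Section 8.3.1 requires a report only if the investigator happens to learn of a serious event and considers it related.

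None of these is a scheduled contact that would find a new event on Days 36 to 42.

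**The Day 28 sentence.** Day 28 ±3 is Day 25 to Day 31, which is 24 to 30 days after dose. An on-time visit is at 28 − 1 = 27 days. The 28 elapsed days described in Section 4.2 are reached only at Day 29 to 31, 3 of the 7 permitted days.

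**The case against.** **Section 8.3.1 binds the site whatever the visit window says.** On this reading a site that makes an early final contact must still collect events up to 42 days. That is a fair reading, and it is why the finding is an inconsistency and not a plain omission. It does not remove the problem, because the schedule provides no contact at which to do it and Section 8.3.1 itself ends active seeking once participation is over.

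**The one-day shortfall of an on-time visit comes from Day 1 numbering.** This stands as far as the endpoint goes: a Day 42 contact leaves no endpoint day unobserved. It remains a mismatch with the wording of Section 8.3.1.

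**A stronger reading is tempting:** that the schedule fails to deliver the 42 days, and that event frequencies are therefore biased low, with delayed thrombosis or antibody-related hypersensitivity missed. The documents do not support that. Contacts on Day 43 to 49 satisfy both periods. Nothing in the documents shows events clustering on Days 36 to 42. The longest half-life visible in Protocol Section 2.2.3.2.1 is 122 hours, in one participant, and 34 days is 34 × 24 = 816 hours, or 816 / 122 = 6.7 such half-lives. Any bias is only potential and depends on when contacts actually occur. A reader might also infer that the early side of the window undoes the purpose of the Day 42 visit. The amendment table gives a safety-monitoring reason for extending the event rows, but the reason for adding the visit itself is blacked out, and SAP Section 2.2 foresees that it may coincide with screening for the Phase 3 study.

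**The analysis is descriptive, with about 6 participants and no hypothesis.** True. No test is affected, but the frequency being described is the primary endpoint.

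**Conclusion.** The inconsistency is real and stands in the current text. The schedule permits, but does not guarantee, the Section 8.3.1 minimum and the Day 1 to 42 window used for the primary endpoint and the bleeding summary. The exposure is at most 7 of 42 endpoint days per participant, and at most 8 days against the 42-day minimum. Both are ceilings that apply only to a contact on Day 35. An on-time contact loses no endpoint days and is one day short of Section 8.3.1.

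This rests on two assumptions: that study days are numbered as the schedule's hour marks imply, and that a final visit inside its window completes participation under Section 4.4.

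The Day 28 matter is secondary. A rationale sentence in Section 4.2 does not match the visit window, but no endpoint requires 28 elapsed days. The point is worth correcting because it touches a primary safety endpoint and the correction is cheap; it does not undermine the study.

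**What to change.** 1. **Schedule of Activities and Section 8.3.1.** Reconcile the two. Remove the early side of the window for the final adverse event and bleeding contact, so that it falls no earlier than Day 42, which secures the endpoint window. If the 42-elapsed-day wording of Section 8.3.1 is kept, the contact must fall no earlier than Day 43 (42 + 1). Otherwise, align Section 8.3.1 with Day 42.
2. **SAP.** Keep the endpoint as Day 1 to Day 42. Add a listing or summary of the last adverse event contact and the days actually observed for each participant, so that the frequencies in SAP Sections 6.1 and 6.5.4 can be read against true follow-up.
3. **Section 4.2.** Reconcile the 28-day sentence with the Day 28 ±3 window. Do not move the Day 28 visit: its pharmacokinetic, pharmacodynamic and antibody samples serve endpoints defined over Day 1 to Day 28, including the area under the effect curve to Day 28, and a later visit would put the final samples outside them.

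**Cost.** An amendment to one visit window and some wording, a narrower scheduling window for sites, and one additional SAP output. No visit, procedure or blood draw is added, and the contact can still be by telephone. A final visit combined with Phase 3 screening could no longer take place before Day 42. The primary endpoint definition does not change.
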